H3b: We will measure a behavioral indicator of connectedness (quality and quantity of positive social interactions), a psychological indicator of connectedness (loneliness), and indicators of well-being over the course of treatment and at 6-month follow-up to estimate the length of treatment needed for improvement; to estimate the proportion of participants who respond to treatment; and the proportion who maintain gains after treatment (to inform a fully powered, randomized efficacy trial).

II. CHARACTERISTICS OF THE RESEARCH POPULATION

a) Number of Subjects: We will enroll approximately =30 participants, anticipating n=24 will begin the intervention (considering exclusion criteria, interest in the intervention) and n=20 participants will provide follow-up data and complete a full course of Social Engage. Subjects will be caregivers (age 50 or older) for a community-dwelling family member with ADRD, living with (or in close proximity to) the family member with dementia. They will be recruited from the IRB approved Health Aging Research Program (HARP) Population Study (RSRB00068059) (see III-d Recruitment Procedures) and Research Match.

b) Gender, Age, Racial, and Ethnic Origin of Subjects:

Women will be well-represented in this study. Caregivers in the US are more likely to be women (67%); Caregivers are also more likely to be white, non-Hispanic (67%), while 10% are African American and 8% are Hispanic. Using the 2018 Alzheimer's Disease Facts and Figures along with our local demographic distributions, we plan to target 25% minority and 67% women enrollment. We will proactively recruit minority participants (including targeting men for enrollment, as they represent the gender minority in the caregiver population) using best practices for minority recruitment, including working with providers serving minorities; collaborating with community gatekeepers; tailoring the recruitment materials to the culture and education level in inner city populations.

Our planned recruitment is as follows:

Racial Categories	Ethnic Categories				Total	
	Not Hispanic or Latino		Hispanic or Latino			
	Female	Male	Female	Male		
American Indian/ Alaska Native	0	0	0	0	0	
Asian	0	0	0	0	0	
Native Hawaiian or Other Pacific Islander	0	0	0	0	0	
Black or African American	4	1	0	0	5	
White	13	9	2	0	24	
More than One Race	1	0	0	0	1	
Total	18	10	2	0	30	

c) Inclusion Criteria (assessed at the HARP screening assessment):

1. Age \geq 50 yrs;
2. English speaking;

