3. Caregiver for a community-dwelling family member with ADRD, living with (or in close proximity to) family member with dementia;

4. Endorse elevated caregiving distress as measured by a score of greater than 11 on the 10-item Perceived Stress Scale (PSS-10) and/or a score of 5 or greater on the Modified Caregiver Strain Index (MCSI);
5. Endorse clinically significant loneliness as measured by a score of greater than 6 on the UCLA Loneliness Scale: Short Form.
6. Has access to e-mail in order to complete the e-consent module in REDCap which will be used in this study.

d) Exclusion Criteria (assessed at the HARP screening assessment):

1. Primary language is not English;
2. Recent or current psychosis;
3. Significant cognitive impairment on a cognitive screening measure at the HARP screening assessment;
4. Hearing problems that preclude completion of the intervention.

e) Vulnerable Subjects: Individuals who are 50 years of age and older with social risk factors for poor mental and physical health outcomes will be included. The results of this study will inform future research and clinical interventions aimed at improving mental health treatment for older caregivers.

III. METHODS AND PROCEDURES

a) Design: This study is a single-arm clinical trial of Social Engage psychotherapy. We will enroll n=30 participants. Participants will complete up to 8 weekly individual Social Engage psychotherapy sessions by Zoom. Participants will be allotted up to 3 months to complete all sessions, a time-frame that allows for two weeks without meeting to address life stressors such as illnesses that may pop up. The first and last session are longer – up to 60 minutes if needed. Middle sessions are shorter (20-45 minutes). Participants will complete follow-up assessments at 3-months (phone/Zoom and online via REDCap) and 6-months (online via REDCap or by phone).

The study team will remain vigilant about any further changes that need to be made to study procedures if there are changes to the research reboot guidance found here:

<https://www.urmc.rochester.edu/coronavirus/coronavirus-research/guidance-for-researchers/human-subjects-research.aspx>

b) Intervention Setting: The assessments and intervention will be remote by phone/Zoom/online.

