e) Assessment Measures & Administration Schedule: All baseline measures will be administered as part of screening through the HARP studies (described above). The following list specifies the assessment measures we propose to collect at follow-up assessments, with assessments conducted at both 3 and 6 month follow-up unless otherwise specified:

Domain 1, Social connectedness: Loneliness scales (UCLA Loneliness Scale and DeJong Loneliness Scale); Berkman-Syme Social Network, Unidimensional Relationship Closeness Scale, *PROMIS social functioning* computerized adaptive tests (satisfaction with roles/activities, social isolation, meaning/purpose, companionship, emotional support, instrumental support).

Domain 2, Caregiving: *Montgomery Borgatta Caregiver Burden Scale*, Modified Caregiver Strain Index (MCSI), Caregiver Reaction Scale

Domain 3, Health indicators: WHODAS, PROMIS computerized adaptive tests of depression, anxiety, fatigue and pain interference; Modified Cornell Services Index (only 3 month); Neuropsychiatric Inventory (only 3 month), FAST (only 3 month) Modified Barthel Index (only 3 month), Columbia Suicide Severity Rating Scale (only 3-month).

Domain 4, Well-being indicators: WHOQOL-BREF is a 36-item measure of several domains of health related quality of life

Domain 5, Mechanisms of behavior/social connectedness change. *Interpersonal Needs Questionnaire (INQ)*; the PSS-10 measures perceived stress.

Domain 6, Feedback about intervention

Participations will be provided an opportunity to discuss what they liked and did not like about the intervention, including what aspects they found helpful. This part of the 3 month interview will be recorded on Zoom. A short self-administered feedback questionnaire will be completed at 6 month follow-up.

f) Study Conditions: This study is a single-arm clinical trial of Social Engage psychotherapy. [name] conducted a study at URMC (K23MH096936) using Social Engage psychotherapy that demonstrated increases in well-being and social engagement for lonely older adults. Social Engage psychotherapy involves psychoeducation on the importance of social connections for health as well as structured goal setting for increasing social

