Aim 3 is to obtain evidence for a signal for efficacy with regards to social connectedness. Baseline data from the assessment battery will be used: a behavioral indicator of social connectedness (quality and quantity of positive social interactions), a psychological indicator of connectedness (loneliness), mechanisms of change (autonomy, competence, and relatedness), and indicators of well-being (psychological distress and quality of life). Assessments will be completed at the end of intervention (3 months), and 6-month follow-up. Follow-up data will be used to estimate the length of treatment needed to demonstrate improvement and to estimate the proportion of participants who demonstrate increases in social connectedness by the end of the intervention and the proportion who maintain gains after the intervention. Our hypotheses will be tested with repeated measures ANOVAs with the Stata software package; significant increases support a signal for efficacy.

h) Data and Safety Monitoring Plan: See Data and Safety Monitoring Plan document.

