This is a Stage One (NIH Stage Model) intervention development study. Aim 1 examines feasibility of Social Engage psychotherapy for caregivers; Aim 2 explores which behavioral strategies are most useful for caregivers when completing Social Engage psychotherapy; Aim 3 is to examine potential efficacy of Engage by examining satisfaction with the intervention and changes in social connectedness over the course of therapy. For Aim 3, we will measure a behavioral indicator of connectedness (quality and quantity of positive social interactions), a psychological indicator of connectedness (loneliness), and indicators of well-being at baseline, 1 month, end of treatment (3 months), and 3 months after completing treatment (6 month follow-up) to estimate the length of treatment needed for improvement; to estimate the proportion of participants who respond to treatment; and to examine the durability of the effect (to inform a fully powered, randomized efficacy trial).

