Participants will be characterized at baseline with regards to demographic characteristics, degree of social disconnectedness, caregiver distress, well-being (depressive symptoms, quality of life), cognitive function, and relationship satisfaction with the person they care for. For Aim 1 the number of subjects and the number of sessions completed by each will be examined to determine if at least 80% of subjects will be willing to start Social Engage and at least 75% complete a full dose of the intervention. Aim 2 is to determine the most useful barrier strategies to use with caregivers. We will tabulate how often each strategy is used within and across participants. Qualitative analyses will be conducted with interview data from participants at follow-up regarding their perceptions of effective barrier strategies (Aim 2) and effective/ineffective aspects of the therapy in general (Aim 3). Aim 3 is to obtain evidence for a signal for efficacy with regards to social connectedness. Baseline data from the STAR core battery will be used: a behavioral indicator of social connectedness (quality and quantity of positive social interactions), a psychological indicator of connectedness (loneliness), mechanisms of change (autonomy, competence, and relatedness), and indicators of well-being (psychological distress and quality of life). Assessments will be repeated after 1 month, the end of intervention (3 months), and at 6-month follow-up. Follow-up data at one month will be used to estimate the length of treatment needed to demonstrate improvement; follow-up data at the end of treatment will be used to estimate the proportion of participants who demonstrate increases in social connectedness by the end of the intervention; and follow-up data at 6-months will be used to demonstrate the proportion of participants who maintain gains in connectedness after completing the intervention (and interacting with the study therapist).

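### The protocol keeps the aim of estimating how long treatment must last, but lists no outcome assessment during treatment; the SAP relies on a 1-month assessment the protocol does not have

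*Protocol*

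**What the plan says.** Hypothesis H3b (protocol section I) says the study will measure social interaction, loneliness and "indicators of well-being over the course of treatment and at 6-month follow-up to estimate the length of treatment needed for improvement". It also names the proportion who respond and the proportion who keep their gains, all to inform a randomised efficacy trial. Section III.g repeats the first of these: "Follow-up data will be used to estimate the length of treatment needed to demonstrate improvement".

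The protocol's schedule is the same wherever it appears. Section III.e says of baseline: "All baseline measures will be administered as part of screening through the HARP studies". It introduces the follow-up battery "with assessments conducted at both 3 and 6 month follow-up unless otherwise specified", and the stated exceptions are measures taken only at 3 months and the feedback items. Section III.g says: "Assessments will be completed at the end of intervention (3 months), and 6-month follow-up". Section III.a (Design) gives the same two follow-up times, and section VII.8 pays for those two only.

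The SAP (Statistical Design & Power: Study 2) lists four times for Aim 3: baseline, 1 month, 3 months and 6 months. Its last paragraph gives each follow-up a job, and for the first it says: "Follow-up data at one month will be used to estimate the length of treatment needed to demonstrate improvement". The SAP is dated 6/30/2019 and the protocol 12/16/2020.

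**The concern.** To estimate how much treatment is needed before improvement appears, the outcome has to be observed at least once while treatment is under way. The protocol keeps the objective but lists no such observation. The only assessment that could serve it is in the SAP, and the later protocol does not carry it.

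Followed exactly, the protocol can report who had improved by 3 months and how many sessions they attended. It cannot report when in treatment the improvement appeared, although this is one of the quantities meant to shape the next trial. Outcomes not collected during treatment cannot be recovered afterwards. The two documents also describe different visit schedules.

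**Working it through.** The plan gives no figure to reproduce here. The check compares the two schedules and works out what each can distinguish.

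**Step 1. Outcome times side by side.**

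| | Protocol (I, III.a, III.e, III.g, VII.8) | SAP |
|---|---|---|
| Baseline | yes | yes |
| 1 month | no | yes |
| 3 months (end of treatment) | yes | yes |
| 6 months | yes | yes |
| Strictly between baseline and 3 months | 0 | 1 |
| Source of the treatment-length estimate | follow-up data, time not stated | 1-month data |

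**Step 2. What can be told apart.** Take participants who improve during treatment and stay improved. With *k* outcome times strictly inside the treatment period, the start of improvement can be placed in one of *k* + 1 intervals. Protocol: 0 + 1 = 1 interval, so everyone looks the same. SAP: 1 + 1 = 2 intervals, by 1 month or later.

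**Step 3. Where the 3-month assessment falls.** Inputs: up to 8 weekly sessions with a two-week allowance (III.a); 1–2 weeks from enrolment to therapy (SAP); 1 month = 365.25/12/7 = 4.35 weeks.

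- Session 8 falls 7 weeks after session 1, or 7 + 2 = 9 weeks with the allowance.
- Three months is 13.0 weeks. Counted from enrolment, that is 13.0 − 1 = 12.0 to 13.0 − 2 = 11.0 weeks after session 1. Counted from session 1, it is 13.0 weeks.

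On the weekly schedule all sessions can be over before the first post-baseline outcome. Participants may take up to 3 months, so if the assessment is counted from enrolment, a slow finisher could be measured shortly before the last session. That is still one late measurement and does not separate early from late improvement.

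**Step 4. Could other protocol data stand in?**

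- H3b speaks of measuring during treatment but attaches no visit to it.
- The checks in sessions 2–8 (Figure 1) concern mood and stress and are not listed outcome measures. Homework review and action plans are session content.
- Session recordings (III.i) are for supervision and for identifying barrier strategies.
- The 3-month feedback interview is analysed qualitatively for Aims 2 and 3.
- Session counts serve Aim 1. Relating them to outcome would set a few low attenders against the rest: 24 × (1 − 0.88) = 2.9 of 24 projected starters at the prior study's rate (at least 6 of 8 sessions), or 24 × (1 − 0.75) = 6.0 under H1b (at least 80% of expected sessions). Those groups are self-selected.

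**Step 5. What the SAP's assessment would give.** One month is 4.35 weeks. Counted from enrolment, that is 3.3 to 2.3 weeks after session 1; counted from session 1, it is 4.3 weeks. Exact (Clopper–Pearson) 95% intervals for the proportion improving early, using the SAP's projected 20 with follow-up and illustrative counts: 5/20, 8.7%–49.1%; 10/20, 27.2%–72.8%; 15/20, 50.9%–91.3%. This is a coarse description only.

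**The case against.** The best case for the plan starts from the dates. The protocol is the later document, and its Aim 3 text follows the SAP's closely but without the 1-month references. The visit may have been dropped on purpose, leaving one consistent schedule in the current protocol and a leftover phrase. Staff working from the protocol would then face little ambiguity. That is a fair reading, though neither document states it. It does not rescue the objective, which remains in both documents without a data source in the protocol.

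A second argument is that required treatment length need not mean timing of improvement. Treatment is up to 8 sessions, attendance is counted, and 3-month change could be described by sessions received. The protocol does not specify this analysis, and with roughly 3 to 6 people below a full course it would be a confounded comparison. It does not answer the question asked.

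Third, this is a Stage One development pilot, and its feasibility, response and maintenance estimates are untouched. That limits the severity. It does not remove the point, because informing the next trial is H3b's stated purpose.

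**Conclusion.** The concern holds. The protocol schedules 0 outcome assessments between baseline and the 3-month end of treatment, against 1 in the SAP. One of H3b's three stated quantities cannot be produced under the protocol as written. More participants or the planned repeated measures ANOVA would not help, because the timing is never observed.

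This conclusion rests on the documents' visit lists and on no assumed figure. The intervals in the working are illustrations. Response at 3 months, maintenance at 6 months and session completion stand. The point should be fixed, but it does not threaten the study as a whole.

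**What to change.** Put one visit list in both documents and choose one of two options.

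**Option 1: keep the objective.** Add the SAP's 1-month assessment to protocol sections III.a, III.e and III.g as a short REDCap form with a connectedness scale from the existing battery.

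- State whether 1 month counts from enrolment or from session 1.
- Define improvement; neither document gives a threshold.
- Report the early/late split descriptively with an exact interval.
- Review section VII.8, which provides payment for the 3- and 6-month assessments only.

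On choice of scale: eligibility uses the UCLA short form, so early change on it will include regression to the mean in a single-arm study, as will change at 3 months. The expected fall is (1 − r) × mean z above the cutoff. The documents give no inputs. Assume normal scores, no treatment effect, one selection on the same scale, 10%–30% of those screened above the cutoff, and test–retest correlation r of 0.6–0.8. The fall then runs from 0.2 × 1.159 = 0.23 SD to 0.4 × 1.755 = 0.70 SD. A scale not used for eligibility, such as the DeJong scale in the follow-up battery, would reduce this but not remove it. Its collection at baseline should be confirmed first, because the protocol does not itemise the baseline measures.

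Cost: a minor amendment and a brief extra online form per participant, for a coarse split that is not a session-level estimate.

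**Option 2: drop the objective.** Delete the treatment-length estimate from H3b and section III.g, and from both SAP paragraphs on Aim 3. Remove the 1-month assessment from the SAP, and limit that part of Aim 3 to response at 3 months and maintenance at 6 months. Cost: wording only, and the loss of one stated sub-objective.

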c) Recruitment Setting and Procedures: Subjects will be recruited via the IRB approved HARP Population Study (RSRB00068059), a research registry run by the current study's Investigators. In compliance with procedures of the Population Study protocol, subjects of the Population Study consent to allow HARP Population Study researchers to share subjects' identifiable data (both name and contact information) with investigators conducting HARP research at the University of Rochester; in addition, they consent to allow their data collected as part of the Population Study to be included in their research record for subsequent HARP studies they participate in, including the current study. All eligible participants will be given information about this study at their HARP in-person assessment. Contact information is collected and maintained via the IRB approved HARP Database Study. A brochure describing the study will be given to participants in the HARP Population study (brochure is uploaded in the rsrb online application). Information about the study will also be posted on the PI's URMC lab webpage (content to be displayed is uploaded in the rsrb online application) and the URMC Clinical Trials website. Information about this study will also be provided in the ResearchMatch registry. We will utilize a REDCap eligibility screening survey given the relatively low base rate of loneliness, which is our key inclusion criteria, to increase the efficiency of our screening/enrollment process. Information about the study will be provided at the beginning of the survey. Individuals who complete this survey and endorse loneliness (UCLA Loneliness Scale) and at least mild stress will have the option to provide their contact information to share with the Healthy Aging Research Program (HARP) staff to complete the HARP Database (RSRB00067245) and Population Study (RSRB00068059) assessments, which will provide information needed to determine final eligibility for this Engage Coaching study, which is

part of the Rochester Roybal Center for Social Ties & Aging Research. The link to the eligibility screen will be available via research match, the URMC Clinical Trials website, and the URMC website with information about the study.

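### Aim 3 counts significant pre-post improvement as support for efficacy in a single-arm study, although UCLA loneliness is both an entry score and a follow-up outcome and is expected to fall with no treatment effect

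*Protocol*

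**What the plan says.** Protocol III.g sets the test and the rule for Aim 3: "Our hypotheses will be tested with repeated measures ANOVAs with the Stata software package; significant increases support a signal for efficacy". The SAP names no test.

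Four other provisions bear on that rule:

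- **Entry (Protocol II.c, criterion 5):** "Endorse clinically significant loneliness as measured by a score of greater than 6 on the UCLA Loneliness Scale: Short Form".
- **Baseline (Protocol III.e):** "All baseline measures will be administered as part of screening through the HARP studies". The score that admits a participant is therefore also the baseline score.
- **Follow-up (Protocol III.e, Domain 1):** at 3 and 6 months the measures include "Loneliness scales (UCLA Loneliness Scale and DeJong Loneliness Scale". Neither scale is marked as deciding. Criterion 5 specifies the short form; Domain 1 does not say which form is used.
- **Pre-screen (Protocol III.c):** an online survey comes before the full screening for some recruits. "Individuals who complete this survey and endorse loneliness (UCLA Loneliness Scale) and at least mild stress" may go forward. No cut-off is given for this step.

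On numbers, Protocol II.a enrols about 30, "anticipating n=24 will begin the intervention (considering exclusion criteria, interest in the intervention) and n=20 participants will provide follow-up data". Neither document says which of these groups Aim 3 analyses.

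On visits, the SAP measures "at baseline, 1 month, end of treatment (3 months), and 3 months after completing treatment (6 month follow-up". The Protocol schedule has only 3 and 6 months after baseline. Both documents give the visits estimation purposes: improvement by the end of treatment, maintenance afterwards and, in the SAP, the length of treatment needed from the 1-month data.

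**The concern.** People admitted because a score is high will, on average, score lower when measured again, because part of a high score is temporary. A control arm would show the same fall and it would cancel. Here there is none, and the stated rule reads a significant improvement as support for efficacy. Protocol III.c itself describes loneliness as having a fairly low base rate, so selection is from the upper part of the distribution, where this effect is largest.

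What is left open adds to the problem. The constructs are listed, but no scale decides. No listed scale is tied to the behavioural indicator. No contrast is attached to the ANOVA. The analysis set could be 24 starters or 20 with follow-up. The rule speaks of increases, whereas improvement in loneliness is a decrease.

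The stated purpose of Aim 3 is to inform a randomised trial. A fall produced by selection could enter that trial's planning as an expected effect.

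**Working it through.** **1. The plan's own number.** The SAP expects 24 starters and attrition of 20% (conservative) or 15% (more likely). 24 × 0.80 = 19.2 and 24 × 0.85 = 20.4, so the stated 20 with follow-up is consistent. I use n = 20.

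**2. Inputs.**
- From the documents: entry on UCLA above a cut-off, baseline equal to the entry score, UCLA repeated at 3 and 6 months, no control arm, n = 20.
- Assumed, because the documents give no figure: share q of the source population above the cut-off, 20% or 40%; retest correlation r between any two occasions, 0.6 to 0.9; normal scores; the same UCLA form throughout; two-sided alpha 0.05; treatment effect exactly zero.

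**3. Expected fall.** With cut-off c on the standard normal scale, the mean entry score of those admitted is φ(c)/q, and the expected fall at retest is (1 − r) × φ(c)/q in population SDs.
- q = 20%: c = 0.842, φ(c) = 0.280, ratio 1.400. Fall = 0.4 × 1.400 = 0.56 at r = 0.6, and 0.1 × 1.400 = 0.14 at r = 0.9.
- q = 40%: c = 0.253, φ(c) = 0.386, ratio 0.966. Fall = 0.4 × 0.966 = 0.39 at r = 0.6, and 0.1 × 0.966 = 0.10 at r = 0.9.

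The fall is positive for every r below 1. Only its size depends on q and r.

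**4. How often the rule is met with no effect.** Simulation, 10,000 trials per cell, n = 20. The criterion is a three-visit repeated-measures ANOVA with p < 0.05 and a lower mean at 3 months than at baseline. The pre-screen columns assume that every recruit also passed an earlier UCLA score at the same cut-off.

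| q | r | Fall (SD) | ANOVA met | Fall, pre-screened (SD) | ANOVA met, pre-screened |
|---|---|---|---|---|---|
| 20% | 0.6 | 0.56 | 86% | 0.38 | 52% |
| 20% | 0.7 | 0.42 | 72% | 0.27 | 35% |
| 20% | 0.8 | 0.28 | 52% | 0.17 | 20% |
| 20% | 0.9 | 0.14 | 27% | 0.08 | 11% |
| 40% | 0.6 | 0.39 | 52% | 0.27 | 27% |
| 40% | 0.7 | 0.29 | 39% | 0.19 | 18% |
| 40% | 0.8 | 0.19 | 26% | 0.12 | 12% |
| 40% | 0.9 | 0.10 | 14% | 0.06 | 7% |

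A single directional baseline-to-3-month test (nominal rate 2.5%) gives 15% to 83%, or 8% to 51% with the pre-screen. The problem therefore does not depend on how the ANOVA is read, and a change of test alone does not cure it.

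**5. What a non-eligibility scale buys.** If the outcome were DeJong, with an assumed correlation of 0.5 to 0.7 with UCLA and r = 0.6 to 0.8, the single directional test is met with no effect in 9% to 49% of trials, or 6% to 25% with the pre-screen. Over the same r, UCLA gives 26% to 83%, or 13% to 52%. The DeJong rate returns to about 2.5% only if the two scales share nothing but the stable part of loneliness.

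**6. Analysis set.** If 20 completers gain 0.5 SD and the other 4 of 24 starters do not change, the mean over starters is 0.5 × 20/24 = 0.42 SD. The choice of set moves the estimate.

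**The case against.** **This is a Stage One pilot.** The SAP says so, H3b is framed as estimation, and the claim is only of a signal. That limits the consequence. It does not change the fact that the Protocol itself makes significance the criterion.

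**The sizes rest on assumptions.** This stands. Neither the pass share nor the retest correlation is in the documents, and with high retest correlation and a pre-screen at the same cut-off the rate is only 7%. A matched UCLA form is also assumed. A different form at follow-up would change the size of the fall.

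**The visits are not left wholly open.** This also stands. Protocol III.g and the SAP link improvement to the end of treatment and maintenance to 6 months. A reader might infer that the team is free to pick any visit. The documents support only the narrower statement that these purposes are not carried into the ANOVA.

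**Two further inferences go beyond the text.**
- A reader might suppose that a significant overall F caused by a late gain would be reported as a 3-month gain. The plan does not say this. If the F-test is followed by a significant favourable pairwise test, that error occurs in 2.1% to 2.4% of trials, against 2.5% for a single directional contrast, so there is no harm on that reading.
- A reader might suppose that any one favourable score out of many is enough. No such rule is stated, so an inflated error rate from multiple scales cannot be charged to the plan.

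**The fix is partial.** True: step 5 shows that bias remains. A fresh baseline taken after entry would restore nominal error under this model, but it needs an additional assessment and would not remove natural change over time. This is why the efficacy inference itself has to go.

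**Conclusion.** The concern holds in this form: the Aim 3 rule can return a favourable significant result on UCLA loneliness when therapy has no effect, because the entry score is the baseline and nothing controls for its expected fall. The direction is certain for retest correlation below 1 in an otherwise stable population. The size is not. For n = 20, 20% to 40% passing and retest 0.6 to 0.9, the fall is about 0.10 to 0.56 SD and the rule is met in about 14% to 86% of trials. With a universal pre-screen at the same cut-off, these become 0.06 to 0.38 SD and 7% to 52%. All of this is conditional on UCLA, in a matching form, being the loneliness outcome, which the plan neither says nor excludes.

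It does not follow that any fall the study observes is an artefact, only that this design cannot separate the two. The missing scale, contrast and analysis set are real but secondary. The change should be made; the pilot can go ahead with it.

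**What to change.** In Protocol III.g and the SAP:

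1. Replace the clause that lets significant increases support an efficacy signal with a statement such as: *Uncontrolled pre-post change, including regression to the mean, can inform the randomised trial but does not show efficacy.*
2. Name one deciding connectedness score that is not an eligibility score. DeJong loneliness is an example, provided it is in the HARP baseline battery, which the Protocol does not itemise. State that lower is better, and that this choice reduces but does not remove the bias.
3. Make the baseline-to-3-month change with its 95% CI the main Aim 3 result, in everyone who starts therapy and using all available scores. Make 3 to 6 months the maintenance result. A mixed model is one convenient way to do this, but the choice of model is secondary.
4. Report UCLA and the remaining scales as estimates with CIs. Say which listed scale measures the behavioural indicator.
5. Reconcile the visits. The SAP states "Assessments will be repeated after 1 month, the end of intervention (3 months), and at 6-month follow-up", while Protocol III.e and III.g have no 1-month assessment.

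**Cost.** This is a wording and analysis change with no new data, if the chosen scale is already collected at baseline. Fewer results can be called significant. For a sustained 0.5 SD gain with n = 20 and an assumed visit correlation of 0.5, power is about 56% for the single contrast against 60% for the overall F.
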